#### 1 BACKGROUND

#### 1.1 Scientific Rationale for Treatment of ITP with Rilzabrutinib

Idiopathic thrombocytopenic purpura, now more commonly referred to as immune thrombocytopenia (ITP), is characterized by autoantibody-mediated destruction of platelets and impaired platelet production, which result in thrombocytopenia and a predisposition to bleeding associated with morbidity and mortality.

15 May 2024

Version number: 1

In general, pharmacotherapy (corticosteroids, intravenous immunoglobulin [IVIg], or anti-D) is used for symptomatic patients with low platelet counts for reducing platelet destruction. While a majority of patients respond initially to corticosteroids, the rate of continued remission is low. Second line therapies include rituximab and splenectomy and are associated with risk of sepsis and immune suppression. Thrombopoietin (TPO) mimetics (6) are approved for the treatment of patients with chronic ITP who have not had sufficient responses to corticosteroids, IVIg, or splenectomy. Novel, safe, and effective oral treatments in this setting to maintain platelet counts would be a significant therapeutic advantage. Thus, there remains a high unmet medical need for novel, safe, and effective oral therapies for ITP.

There is preliminary evidence to support the role of Bruton tyrosine kinase (BTK) inhibition in patients with autoimmune cytopenias (2, 3), where sequential episodes of severe autoimmune hemolytic anemia and ITP ceased after initiation of treatment with ibrutinib, a BTK/EGFR/ITK inhibitor, in patients with chronic lymphatic leukemia (CLL).

Rilzabrutinib is a high-affinity inhibitor of BTK. rilzabrutinib treatment *in vitro* profoundly inhibited human B cell activation and blocked antibody (IgG, IgE) mediated activation of immune cells via Fc receptor signaling. In nonclinical studies, rilzabrutinib demonstrated a significant dose dependent reduction of platelet-loss (consumption) in a mouse model of immune thrombocytopenia. Rilzabrutinib also showed rapid and significant anti-inflammatory effects in rat collagen-induced arthritis model, rat antibody mediated arthus model, spontaneous canine pemphigus foliaceus and human pemphigus vulgaris (PV).

#### 1.2 Summary of Rilzabrutinib Clinical Experience

To date, rilzabrutinib has been administered to more than 170 healthy volunteers and patients in Phase 1 and Phase 2 studies. Rilzabrutinib has been generally well tolerated. In the completed Phase 2 study, PRN1008-005 (NCT02704429), a total of 41 patients with pemphigus were enrolled, 27 patients in Part A (12 weeks of rilzabrutinib and 12 weeks of follow-up) and 15 patients in Part B (24 weeks of rilzabrutinib and 4 weeks of follow-up). One patient was enrolled in Part A, then enrolled in Part B 5 months after completing Part A. In Part A, doses ranged from 400 mg to 600 mg BID. In Part B, doses included 400 mg QD, 400 mg BID, and 600 mg BID. In Part A, 51.9% of patients achieved the primary control of disease activity (CDA) endpoint at the Week 5 visit, and 70.4% at the Week 13 visit, further improving to 85.2% after an additional follow up of 12 weeks off rilzabrutinib treatment. Complete response rates were observed beginning at the Week 13 visit in 4 patients, increasing to 6 patients by 20 weeks. In Part B, rilzabrutinib delivered high CDA rates with rapid onset independent of dose with 60.0% of patients achieving CDA at the Week 5 visit and 86.7% within 12 weeks of treatment.

[figure not shown]
Escalation to a dose of 400 mg BID and longer treatment to 24 weeks led to CR rates of 33.3%. Further results are provided in the PRN1008-005 clinical study report (5). Preliminary results of PRN1008-010 after 47 patients were enrolled (05 May 2020 data cutoff) were presented at European Hematology Association annual meeting (7).

Analysis of hematology and coagulation measurements in prior healthy volunteer studies showed
1.3 Clinical Pharmacokinetics and Pharmacodynamics of Rilzabrutinib
Rilzabrutinib is rapidly absorbed following oral administration, with a fast half-life (3–4 hours), and variable pharmacokinetics (PK).
()/-

Rilzabrutinib demonstrates a slow BTK off-rate, with BTK occupancy observed for more than 24 hours after plasma concentrations are undetectable. With multiple dosing, equivalent doses of 428 mg of the immediate-release (IR) tablet and above (QD or BID) appear to achieve near maximal peak BTK occupancy, however twice daily dosing regimens maintained higher occupancy at trough compared to once daily dosing.

### 2 DOSE RATIONALE AND STUDY DESIGN

#### 2.1 Rationale for the Study Design

15 May 2024

[figure not shown]
Version number: 1

Patients enrolled in this study will have low platelet counts having relapsed on or been refractory to prior therapies with no available and approved therapeutic options, and may continue corticosteroids and/or thrombopoietin mimetics during the study. Compared to a sequential group dose-escalation study, this design will not expose the initial cohorts of patients to ineffective dose levels for a prolonged period and will thus potentially minimize the use of rescue medication.

The active treatment period of 24 weeks and the post-treatment follow up period of 4 weeks and the Long Term Extension (LTE) are justified by safety and efficacy seen to date in human and animal studies. The "sentinel cohorts" at each dose level consist of the first 3 patients, or 6, if 3 extra are added for a dose-limiting toxicity (DLT) or platelet response (as defined in the primary endpoint and sustained for at least 3 of 4 consecutive counts over one or two 28-day cycles). To be evaluable in a sentinel cohort, patients must have ≥75% compliance over the 28-day dosing period. The sentinel cohort data is reviewed for by the Independent Data Safety Monitor (IDSM, who is also Chairperson of the Safety Monitoring Committee [SMC]), in order to choose the starting dose for additional, new patients entering the study. After safety review, the IDSM may determine that a starting dose for new patients should be dropped for futility (lack of platelet response), increased to the next planned dosing level, kept the same or reduced (Section 4.4).

Patients will be monitored frequently by weekly platelet counts and complete blood counts (CBCs) throughout the active treatment period and will continue in the LTE weekly for 6 months, then monthly for six months, and every three months thereafter. PK samples will be collected intensively on the first day of each new, higher dose level and at random times following dosing at each on-treatment follow up visit. The other clinical and laboratory assessments used in this study are standard and used in clinical practice for assessment of patients with ITP. The bleeding assessment (Idiopathic Thrombocytopenic Purpura Bleeding Scale [IBLS]) (9) has been used in prior studies.

# 2.1.1 Rationale for Doses Used and Duration of Study Part A

Pemphigus vulgaris is an autoantibody-driven disease like ITP. In Study PRN1008-005 a rapid onset of clinical effect was seen in most pemphigus patients within 4 weeks, with continued improvement to very low levels of skin inflammation by the end of 12 weeks of therapy. Therefore 28-day cycles to assess the initial platelet response, and trigger intrapatient dose-escalation are appropriate. A 24-week overall treatment period is preferred for this dose-finding study to enable all patients to potentially dose-escalate to the higher doses and be fully evaluated at those doses.

A 24-week treatment period and the LTE are supported by completed long term Good Laboratory Practice (GLP) animal safety toxicology studies, and a favorable risk benefit profile observed in completed and ongoing human studies (4).

# 2.1.2 Rationale for Doses Used and Duration of Study Part B

The dose-finding portion of the study (Part A) has been completed. All doses were evaluated and the 400 mg BID dose has been selected as a safe and efficacious dose for further investigation in Part B. Similar to Part A, there will be a 24-week treatment period to assess the primary endpoint and an LTE for patients who demonstrate a platelet response.

The primary endpoint in Part B will assess the durability of response in the last 12 weeks of the 24-week treatment period, and a key secondary endpoint will assess the platelet response in the first 8 weeks of treatment for the achievement of the primary endpoint.

#### 2.2 Overall Benefit-Risk Assessment

#### Safety Profile

Rilzabrutinib was well tolerated in the clinical development program, including single and multiple doses. The most common treatment-emergent adverse events (TEAEs) were \_\_\_\_\_\_\_ The majority of TEAEs were mild to moderate in severity.

Until 02 January 2024, no SUSAR has been reported in the ITP Phase 2 PRN1008-010 Study. There was one SUSAR of serious infection reported in the ongoing ITP Phase 3 Study (PRN1008-018), and a causal association with blinded IMP (rilzabrutinib/placebo) was deemed

unlikely by the Sponsor. No major bleeding events occurred in the clinical experience with rilzabrutinib. Refer to the Investigator's Brochure for additional and updated information.

#### Risk Assessment

Based on the review of the cumulative data, as of 2 January 2024, with an estimated exposure of 1137 participants who received at least one dose of rilzabrutinib or placebo (826 participants on rilzabrutinib with approximately 545 patient-years, estimated based on randomization ratio) across multiple disease conditions, there are following are considered as important potential risks for rilzabrutinib:

•

Details of important potential risks together with a summary of the cumulative clinical safety data are provided below.

Table 1 - Risk assessment

15 May 2024

#### Benefit assessment

Patients with ITP were expected to only transiently benefit from rilzabrutinib with the initial dose escalation scheme and 12-weeks of treatment, although anecdotal evidence from the Phase 2 study of rilzabrutinib in pemphigus suggests a durable effect post-treatment may occur in some patients. The additional non-clinical data supported longer treatment durations enabling amending to 24 weeks of treatment and allowing dose escalation to the highest dose level, as well as an LTE for patients with platelet response.

Preliminary review of the efficacy data in Part A of this study demonstrated a dose response and that patients with ITP who failed multiple treatments were able to achieve a fast and durable platelet response at the 400 mg BID dose of rilzabrutinib. Patients treated with once daily doses were less likely to achieve fast platelet response and the primary endpoint (10). This evidence of

treatment effect supports initiation of Part B of the study that will focus on further investigating this dose of rilzabrutinib in this patient population. Preliminary results of Part A and Part B provide evidence that treatment with rilzabrutinib 400 mg BID induces a rapid and durable platelet response and continued to be well tolerated in patients with ITP (11, 12).

**Benefit-risk:** To date, preliminary analyses of efficacy and safety in patients with ITP support an overall favorable benefit-risk profile, and to continue the development of rilzabrutinib for patients with ITP.

#### 3 OBJECTIVES AND OUTCOME MEASURES OF THE STUDY

# 3.1 Objectives of the Study: Part A

# 3.1.1 Safety Objective

• To characterize the safety and tolerability of up to four dose levels of rilzabrutinib in patients with ITP

15 May 2024

Version number: 1

## 3.1.2 Efficacy Objectives

- To explore the clinical activity of up to four dose levels of rilzabrutinib in relapsed/refractory patients with ITP
- To identify a potential dose regimen to use in future studies of rilzabrutinib in patients with ITP

#### 3.1.3 Pharmacokinetics Objective

• To characterize the pharmacokinetics of rilzabrutinib in patients with ITP

# 3.1.4 Exploratory Objectives

- To explore effect of rilzabrutinib on thrombopoietin (TPO) levels
- To explore effect of rilzabrutinib on quality of life (QOL) using the

of rilzabrutinib

# 3.2 Objectives of the Study: Part B

#### 3.2.1 Safety Objective

• To characterize the safety and tolerability of 400 mg BID dose of rilzabrutinib in patients with ITP

#### 3.2.2 Efficacy Objectives

- To further explore the clinical activity and durability of response of the selected dose of 400 mg BID of rilzabrutinib in patients with ITP who have relapsed or have an insufficient response to prior therapies
- To evaluate the predictive value of platelet response to rilzabrutinib therapy in the first 8 weeks of active treatment for the achievement of the primary endpoint

# 3.2.3 Pharmacokinetics Objective

To characterize the pharmacokinetics of rilzabrutinib in patients with ITP

# 3.2.4 Exploratory Objectives

- To explore effect of rilzabrutinib on thrombopoietin (TPO) levels
- To explore effect of rilzabrutinib on quality of life (QOL) using the and Idiopathic Thrombocytopenic Purpura Patient Assessment Questionnaire (ITP-PAQ)

15 May 2024

Version number: 1

# 3.3 Outcome Measures of the Study: Part A

# 3.3.1 Primary Safety Endpoints

Safety will be assessed by the incidence, severity, and relationship of TEAEs, including clinically significant changes in physical examination, laboratory tests, and vital signs. Treatment-emergent adverse events in the post treatment follow-up period will also be assessed and examined for possible relationship to the prior rilzabrutinib treatment. Adverse events (AEs) will be categorized as treatment emergent after the first dose of rilzabrutinib has been received.

# 3.3.2 Primary Efficacy Endpoint

Proportion of patients able to achieve two or more consecutive platelet counts, separated by at least 5 days, of  $\geq$ 50,000/ $\mu$ L AND an increase of platelet count of  $\geq$ 20,000/ $\mu$ L from baseline, by dose level, without use of rescue medication in the 4 weeks prior to the latest elevated platelet count.

Secondary efficacy endpoints are described in Section 10.

# 3.4 Outcome Measures of the Study: Part B

# 3.4.1 Primary Safety Endpoints

Safety will be assessed by the incidence, severity, and relationship of TEAEs, including clinically significant changes in physical examination, laboratory tests, and vital signs. Bleeding TEAEs will be tabulated and a proportion of patients with a Grade 2 or higher bleeding event will be provided.

# 3.4.2 Primary Efficacy Endpoint

Proportion of patients able to achieve platelet counts  $\geq 50,000/\mu L$  on at least 8 out of the last 12 weeks of the 24-week treatment period without the use of rescue medication after 10 weeks of active treatment.

Secondary efficacy endpoints are described in Section 10.

# 4 INVESTIGATIONAL PLAN

# 4.1 Overall Study Design and Plan Part A

This is an adaptive, open-label, dose-finding study of rilzabrutinib in patients with ITP who are refractory or relapsed with no available and approved therapeutic options, with a platelet count  $<30,000/\mu L$  on two counts no sooner than 7 days apart in the 15 days before treatment begins.

15 May 2024

Version number: 1

The active treatment period is 24 weeks and the post-treatment follow up period is 4 weeks.

Once a patient escalates to the 400 mg BID dose in the active treatment period, the patient will stay at this dose for 24 weeks.

Each patient is enrolled in the study and allowed to up-titrate their dose after 28 days of rilzabrutinib therapy at each dose level if they do not experience a platelet response (as defined in the primary endpoint) or a DLT at the last dose level. If they experience a platelet response in the first cycle at any one dose level but do not have a platelet response in the second cycle at that dose, they may dose escalate at the end of the second cycle. Patients experiencing a platelet response (as defined for the primary endpoint) will not have their dose escalated at the next cycle.

The "sentinel cohorts" at each dose level consist of the first 3 patients, or 6, if 3 extra are added for a DLT or platelet response (as defined in the primary endpoint and sustained for at least 3 of 4 consecutive platelet counts at any dose level). To be evaluable in a sentinel cohort, patients must have ≥75% compliance over the 28-day dosing period. The sentinel cohort data is reviewed by the IDSM, in order to choose the starting dose for additional, new patients entering the study. After review, the IDSM may determine that a starting dose for new patients should be dropped for futility (lack of platelet response), increased to the next planned dosing level, kept the same or reduced (Section 4.4).

Doses levels will be: 200 mg QD; 400 mg QD; 600 mg per day (300 mg BID); 800 mg per day (400 mg BID) (see table below). Due to the design, not all patients will necessarily be dosed at all dose levels.

# **Adaptive Cohort Dosing Table**

Cohort	Starting dose level (n*) 4 weeks	Next dose level** 4 weeks	Next dose level** 4 weeks	Next dose level**	Next dose level**	Next dose level**
1	200 mg QD (3-6)	400 mg QD	300 mg BID	400 mg BID	400 mg BID	400 mg BID
2	400 mg QD (≤6)	300 mg BID	400 mg BID	400 mg BID	400 mg BID	400 mg BID
3	300 mg BID (≤6)	400 mg BID	400 mg BID	400 mg BID	400 mg BID	400 mg BID
4	400 mg BID (≤6)	400 mg BID	400 mg BID	400 mg BID	400 mg BID	400 mg BID

15 May 2024

Version number: 1

Dose down-titration is permitted where, in the opinion of the Investigator, tolerability is poor and a satisfactory platelet response was seen in that patient on a lower dose previously studied or as mandated by the SMC. Otherwise, patients with clinically significant intolerance to rilzabrutinib should be discontinued from the study.

Patients experiencing a DLT or requiring rescue therapy for low platelet counts must be discontinued from the study.

Patients will be monitored with weekly platelet counts and CBCs throughout the study; PK samples will be collected intensively on the first day of each new, higher dose level and at random times following dosing at each on-treatment follow up visit. Patients will have weekly study visits/laboratory tests throughout the Part A of the study (Schedule of Assessments, Appendix 3).

Patients may enter the study on stable doses of prednisone and/or TPO receptor agonists (TPO-RAs). Other are not permitted.

# Long Term Extension (LTE) Part A and Part B

After completing the active treatment period, patients who respond to rilzabrutinib will be allowed to enter the LTE. A platelet response is defined as platelet count  $\geq 50,000/\mu L$ , or  $\geq 30,000/\mu L$  and doubling of baseline at  $\geq 50\%$  of the visits during the last 8 weeks of the active treatment period (a minimum of 4 visits per the Schedule of Assessments) will be required. Baseline should be calculated as an average of platelet counts used for enrollment per Inclusion Criterion #4.

\* Unless a sustained platelet response is seen or a DLT, in which case 3 extra patients are added to that group. A starting dose level may be dropped for futility after 3 or 6 patients are evaluated, or retained if efficacy is observed.

\*\* Individual patients will not dose-escalate when there is a platelet response at a lower dose level or toxicity (see dose-escalation rules). If several dose levels are therapeutic, some or all patients may not reach the higher dose levels.

A patient may continue in the LTE until:

a) The patient is no longer responding as described in the table below:

Time in the LTE	'No response' platelet counts defined as <30,000/μL or <20,000/μL above baseline based on:		
C1_LTE through C6_LTE	4 consecutive weekly visits		
C7_LTE through C12_LTE	2 consecutive monthly visits		
QX_LTE	1 quarterly visit In this case, a second platelet count has to be obtained in one month to confirm lack of response		

Patients who continue into the LTE will be monitored with weekly platelet counts and CBC's for the first 6 months, and then monthly for an additional 6 months, then once every 3 months with the assessments as outlined in the LTE Schedule of Assessments (Appendix 5 and Appendix 6).

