# Study Design Part B:

This is an open-label study of rilzabrutinib in patients with ITP who have relapsed or have an insufficient response to prior therapies. Eligible patients will have a platelet count  $<30,000/\mu\text{L}$  on two occasions no less than 7 days apart, within 15 days before treatment begins and a platelet count of  $\le35,000/\mu\text{L}$  on Study Day 1 (SD1).

The study consists of a 28-day screening period, 24-week active treatment period, and a long-term extension. After the last dose of rilzabrutinib there will be a 4-week safety follow-up period. Patients enrolled with a positive hepatitis B virus (HBV) core

antibody result and hepatitis B virus surface antibody (HBsAb) titer  $\geq$ 100 IU/L will continue to have HBV DNA monitored monthly for 6 months after treatment has ended.

Patients will have weekly study visits/laboratory tests throughout the study (Schedule of Assessments, Appendix 4).

Long Term Extension (LTE):

After completing the active treatment period, patients who respond to rilzabrutinib will be allowed to enter the LTE. A platelet response for entering the LTE is defined as platelet count  $\geq 50,000/\mu L$ , or  $\geq 30,000/\mu L$  and doubling of baseline at  $\geq 50\%$  of the visits during the last 8 weeks of the active treatment period (a minimum of 4 visits per the Schedule of Assessments) will be required. Baseline should be calculated as an average of platelet counts used for enrollment per Inclusion Criterion #4.

A patient may continue in the LTE until:

a) The patient is no longer responding as described in the table below:

Time in the LTE	'No response' platelet counts defined as <30,000/μL or <20,000/μL above baseline based on:
C1_LTE through C6_LTE	4 consecutive weekly visits
C7_LTE through C12_LTE	2 consecutive monthly visits
QX_LTE	l quarterly visit In this case, a second platelet count has to be obtained in one month to confirm lack of response

In the LTE, patients will be monitored weekly for the first 6 months, monthly for an additional 6 months, then once every 3 months with the assessments as outlined in the LTE Schedule of Assessments Appendix 5 and Appendix 6.

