### 6.2 Part B

### 6.2.1 Inclusion Criteria

- 1. Male or female patients, aged 18 to 80 years old
- 2. Patients with immune-related ITP (both primary and secondary) as defined by current guidelines with at least 3 months duration
- 3. Patients who had a response (achievement of platelet count ≥50,000/µL) to IVIg/anti-D or corticosteroid that was not sustained and failed at least one other ITP therapy (that was not IVIg or corticosteroid)
- 4. Patients with a platelet count of  $<30,000/\mu L$  on two occasions no less than 7 days apart in the 15 days before treatment begins, and no platelet count above  $35,000/\mu L$  on Study Day 1.
- 5. Patients with adequate hematologic, hepatic, and renal function (absolute neutrophil count ≥1.5 × 10^9/L, Hgb >9 g/dL, AST/ALT ≤1.5 × ULN, albumin ≥3 g/dL, total bilirubin ≤1.5 × ULN, eGFR >50 mL/min (Cockcroft and Gault method) (pre-dose may be checked up to Day -3)
- 6. Female patients who are of reproductive potential must agree for the duration of active treatment in the study to use a highly effective means of contraception (hormonal contraception methods that inhibits ovulation, intrauterine device, intrauterine hormonereleasing system, bilateral tubal ligation, vasectomized partner, or true abstinence; when this is in line with the preferred and usual lifestyle of the patient). Unless surgically sterile, postmenopausal females should have menopause confirmed by FSH testing.
- 7. Able to provide written informed consent and agreeable to the schedule of assessments.

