2.1.4 Exploratory Objectives

2.2 Study Design

This is an adaptive, open-label, dose-finding study of rilzabrutinib in patients with ITP who are refractory or relapsed with no available and approved therapeutic options, with a platelet count <30,000/ μ L on two counts no sooner than 7 days apart in the 15 days before treatment begins.

Protocol amendments changed the active treatment period from 12 weeks to 24 weeks to >=24 weeks as follows:

In protocol version 7.0 (01 December 2017) the active treatment period is 12 weeks with a

- post-treatment safety follow up for a period of 12 weeks.
- In protocol version 8.0 (24 August 2018) the active treatment period is 24 weeks with a post-treatment safety follow up for a period of 4 weeks.
- In protocol version 9.0 (06 May 2019), patients who complete the active treatment period and demonstrate a platelet response defined as platelet counts ≥ 50,000/μL at ≥ 50% of the visits during the last 8 weeks of the active treatment would be allowed to enter the Long Term Extension (LTE) to receive study drug at the 400 mg BID dose. Patients may continue in the LTE until the patient is:
 - a) no longer responding per the LTE-defined platelet response and/or experiences dose limiting toxicities
 - b) the drug is no longer being developed by the Sponsor
 - c) the program is stopped for safety reasons or
 - d) the drug becomes commercially available in the patient's country

Patients who had previously completed the study prior to this amendment, were responders per the LTE requirement and did not experience a Dose-Limiting Toxicity (DLT) were allowed to enroll into the LTE. To qualify for the LTE patients would still need to satisfy the protocol inclusion and exclusion criteria.

Each patient is enrolled in the study and allowed to up-titrate their dose after 28 days of rilzabrutinib therapy, at each dose level, if they do not experience a platelet response (as defined in section 6.2 of the protocol) or a DLT at the last dose level. If the patient experiences a platelet response in the first 28-day cycle, at any one dose level but does not have a platelet response in the second cycle at that dose, they may dose escalate at the end of the second cycle. Patients experiencing a platelet response (as defined for the primary endpoint) will not have their dose escalated at the next cycle.

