4.1 GENERAL CONSIDERATIONS

In general, continuous data will be summarized using the number of observations available, mean, standard deviation, median, (Q1, Q3 if applicable), minimum, and maximum. Categorical and ordinal data will be summarized using the count and percentage of participants.

The baseline value is defined as the last available value before the first dose of investigational medicinal product (IMP). For participants enrolled, however not treated, the baseline value is defined as the last available value before enrollment.

Baseline of platelet count is defined as the average of three platelet counts: two qualified screening platelet counts collected in eCRF and Week 1 (study day 1) platelet count.

Observation period

The observation period will be divided into 3 segments:

- The **pre-treatment period** is defined as the period up to date of first investigational medicinal product (IMP) administration.
- The **on-treatment period** is defined as the period from the first dose of IMP to the last dose of IMP + 1. The on-treatment period includes the main on-treatment period and the long-term extension (LTE) on-treatment period.
 - If the subject did not enter LTE, the **main on-treatment period** is defined as from the date of first dose of IMP to the date of the last dose of IMP + 1.
 - If the subject entered LTE, the **main on-treatment period** is defined as from the date of first dose of IMP to the date before the first dose of IMP during LTE. Date of first dose during LTE is based on the date of dosing reported on LTE Cycle 1 Day 1 (C1D1 LTE) in Study Drug Administration eCRF.
 - LTE on-treatment period is defined as from the date of first dose of IMP during LTE to the last dose of IMP + 1.
- The **post-treatment period** is defined as the period from the end of the on-treatment period.

The **treatment-emergent period** is any time after the first administration of rilzabrutinib. Treatment-emergent (TE) period includes both on-treatment period and post-treatment period. That is, **main treatment-emergent period** includes main on-treatment period and post-treatment period for those did not enter LTE; **LTE treatment-emergent period** includes LTE on-treatment period and post-treatment period.

Property of the Sanofi group - strictly confidential

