4.2 PARTICIPANT DISPOSITIONS

The number (%) of participants included in each of the analysis populations listed in Table 3 will be summarized.

Screen failures are defined as participants who consent to participate in the study but are not subsequently enrolled. The number (%) of screen failures and reasons for screen failures will be provided in the screened population.

The number (%) of participants in the following categories will be provided:

- Enrolled participants
- Enrolled but not exposed participants
- Enrolled and exposed participants
- Participants who completed the main study period
 - Participants who completed 12 weeks of treatment
 - Participants who completed 24 weeks of treatment
- Participants who did not complete main 24-week study period and main reason for permanent IMP discontinuation
- Participants who entered LTE
 - Ongoing in LTE
 - Discontinued from LTE and main reason for discontinuation
- Status at the last contact (alive, dead).

In addition, the number (%) of participants screened, screened-failed, enrolled, entered LTE, with early study discontinuation will be provided by country and site.

Protocol deviations

Major protocol deviations will be tabulated by the deviation categories based on enrolled population.

Participants impacted by Covid-19 will be summarized upon data availability, such as discontinuation due to Covid-19, protocol deviation due to Covid-19, and visit(s) impacted by Covid-19 etc. as collected in eCRF.

Page 68

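### Read literally, the per-count threshold for stopping in the LTE lies above the per-count threshold for entering it when baseline is strictly between 10,000 and 20,000/µL, by at most 5,000/µL

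*Protocol*

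**What the plan says.** The rules appear in four places in the protocol: the synopsis (Study Design Part A and Part B), Section 4.1 and Section 4.2.

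- **Entry.** After the active period, "patients who respond to rilzabrutinib will be allowed to enter the LTE". The synopsis ties the definition to that purpose: "A platelet response for entering the LTE is defined as platelet count" of 50,000/µL or more, or of 30,000/µL or more with doubling of baseline. It must be met at 50% or more of the visits in the last 8 weeks, with a minimum of 4 visits.
- **Stopping.** Item a) of the continuation list ends LTE treatment when "The patient is no longer responding as described in the table below". The table heading reads "No response' platelet counts defined as <30,000/μL or <20,000/μL above baseline based on", followed by the persistence needed: 4 consecutive weekly visits in cycles 1 to 6, 2 consecutive monthly visits in cycles 7 to 12, then 1 quarterly visit confirmed a month later.
- **Baseline.** For these rules it is the average of the platelet counts used for enrollment.

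Only item a) is visible in the public text, and this point concerns item a) alone. The two SAPs tabulate why patients left the LTE (Part A SAP 5.1.1; Part B SAP 4.2: "Discontinued from LTE and main reason for discontinuation").

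**The concern.** Entry is judged by a ratio to baseline and stopping by a fixed increment over baseline. Nothing in the documents reconciles the two. An exit bar below the entry bar would be ordinary, since it avoids stopping patients over small fluctuations. Here, for part of the eligible baseline range, the exit bar is the higher one.

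The counts concerned are ones the study treats as response elsewhere. The first secondary endpoint of Part B credits weeks at 50,000/µL or more, or at 30,000/µL or more with doubling of baseline. A count can therefore add to efficacy in the 24-week period and count as 'no response' in the LTE.

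Two things are at stake. A borderline responder may lose access to the drug with no change in condition, and a descriptive table of LTE discontinuations may be read as loss of response where none occurred.

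**Working it through.** **Inputs** (thousands per µL; b = baseline). The entry and stop rules are as above. Eligibility allows the baselines in question: both parts require two screening counts below 30. The plan gives no figure of its own on this point to reproduce.

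**Formulas, per count**

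- Lowest count that meets the entry criterion: E = min(50, max(30, 2b)).
- Lowest count that escapes 'no response', with 'or' taken literally: S = max(30, b + 20).
- Counts from E to just under S meet both definitions whenever S > E.

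**Solving by range of b**

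- b ≤ 10: E = S = 30. No overlap.
- 10 < b ≤ 15: E = 30, S = b + 20. Width b − 10, rising to 5 at b = 15.
- 15 < b < 20: E = 2b, S = b + 20. Width 20 − b.
- b = 20: E = S = 40. No overlap.
- 20 < b < 30: entry is the stricter rule. No overlap.
- b = 30: E = S = 50. No overlap.

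| b | E | S as written | Overlap width | Stop threshold with fix, min(S, E) | Stop threshold with 'and', min(30, b + 20) |
|---|---|---|---|---|---|
| 10 | 30 | 30 | 0 | 30 | 30 |
| 12 | 30 | 32 | 2 | 30 | 30 |
| 15 | 30 | 35 | 5 | 30 | 30 |
| 18 | 36 | 38 | 2 | 36 | 30 |
| 20 | 40 | 40 | 0 | 40 | 30 |
| 25 | 50 | 45 | 0 | 45 | 30 |
| 28 | 50 | 48 | 0 | 48 | 30 |

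**Worked patient.** With b = 15 and steady counts of 32, each count is at least 30 and at least 2 × 15 = 30, so entry is met at every visit. Each count is 32 − 15 = 17 above baseline, which is below 20, so each is 'no response'. Four weekly visits trigger the stop.

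**A small second overlap, in Part B only.** Inclusion Criterion #4 requires two counts below 30 "in the 15 days before treatment begins, and no platelet count above" 35 on Day 1. The Part B SAP (4.1) says "Baseline of platelet count is defined as the average of three platelet counts", Day 1 included. If that baseline is used for the LTE rule, b can reach just under (30 + 30 + 35)/3 = 31.67. For b > 30, E = 50 and S = b + 20, so the width is b − 30, under 1.67.

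**Persistence, as an illustration only.** Assume independent log-normal weekly counts. The chance of being stopped in the weekly phase is then the chance of at least one run of 4 'no response' counts in 24 visits. The medians and log SDs below are assumptions; the documents give none.

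| Baseline, median | Log SD | As written | With fix |
|---|---|---|---|
| 12, 31 (in band) | 0.1 / 0.2 / 0.3 | 84 / 71 / 66% | 24 / 38 / 44% |
| 15, 32 (in band) | 0.1 / 0.2 / 0.3 | 99 / 91 / 82% | 7 / 24 / 33% |
| 18, 37 (in band) | 0.1 / 0.2 / 0.3 | 80 / 68 / 64% | 28 / 41 / 45% |
| 15, 40 (above band) | 0.2 | 6% | 0.1% |

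One cell in full: baseline 15, median 32, log SD 0.2. As written, P(count < 35) = Φ(ln(35/32)/0.2) = 0.673 per visit, and a run of 4 in 24 has probability 0.909. With the fix, P(count < 30) = Φ(ln(30/32)/0.2) = 0.373, and the run has probability 0.242.

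**The case against.** **Two tests for two purposes.** The entry definition is labelled as one for entry and is judged over 8 weeks, while the stop rule needs consecutive failures. A reader might infer that the stop rule as a whole is stricter than the entry rule. The documents do not support that: only the per-count threshold is higher, and one weekly count in four at or above b + 20,000 prevents a weekly-phase stop. The persistence rules do not help a patient whose counts stay in the band.

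**The increment has a basis.** A rise of 20,000/µL over baseline recurs in the study's endpoints, including the Part A primary endpoint, and asking for it to justify open-ended dosing could be deliberate. The protocol does not say so, and admitting patients who never met the increment sits badly with that purpose.

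**'Or' may be a slip for 'and'.** Exploratory measures in both parts define success as at least 30,000/µL or at least 20,000/µL above baseline (Section 10.4). The complement of that uses 'and', which gives no overlap at any baseline. This objection stands as an open question. The text says 'or' in all four places, and 'and' would cut the stop threshold at baseline 25,000 from 45,000 to 30,000/µL, so the intent should be settled rather than assumed.

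**The earlier exit rule.** The Part A SAP (2.2) describes version 9.0 as continuing patients until "no longer responding per the LTE-defined platelet response and/or experiences dose limiting toxicities". A reader might take this as proof that the current rule is a mistake. It describes a superseded rule with an entry bar of 50,000/µL and shows nothing about present intent.

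**Reporting.** A reader might infer that in-band patients will be recorded as having lost response. The SAPs show only that a reason is tabulated, not which labels the CRF offers. Platelet profiles for individual patients are also planned, so the counts would be visible.

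**Conclusion.** The point holds as a minor inconsistency in the rule as written. With 'or' taken literally, counts in a band up to 5,000/µL wide both meet the entry criterion and count as 'no response' for baselines strictly between 10,000 and 20,000/µL. A patient who stays in that band is admitted and then stopped unchanged. The threshold arithmetic is exact; it depends on the literal 'or' and on the baseline as the protocol defines it. The overlap above 30,000/µL depends further on including the Day 1 count.

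The reach is small: LTE retention and descriptive LTE data. The number of patients affected cannot be derived from the documents and may be zero. Part A patients admitted under the version 9.0 rule did not use the doubling arm. All Part B participants had finished 24 weeks by the SAP date of 28 Nov 2022. Adding 12 × 28 days gives 30 Oct 2023, so by inference their weekly and monthly LTE phases ended before the 15 May 2024 protocol.

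A reader might take the 64% to 99% stop chances as expected rates. They are not: they assume a median inside the band. With the median at 40,000/µL the figure is about 6%. Nor does the point touch either primary endpoint, since both are assessed before the LTE.

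**What to change.** First settle whether 'or' or 'and' is meant. If 'and', correct the text in all four places.

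If 'or' is meant, keep the stop wording and add at the next amendment: *and not meeting the LTE entry platelet criterion (≥50,000/µL, or ≥30,000/µL and ≥2 × baseline)*. The stop threshold becomes min(S, E). This removes both overlaps and changes nothing at or below 10,000/µL or from 20,000 to 30,000/µL. Replacing the stop rule by the full complement of the entry rule is not advised: at baseline 25,000 it would raise the threshold from 45,000 to 50,000/µL.

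Meanwhile, flag in the LTE disposition table any patient stopped for 'no response' whose stopping counts met the entry criterion. This needs no amendment and, given the timing, is the more useful step.

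Cost: one clause in four places, with IRB/IEC approval, and health-authority approval if the amendment is substantial (Section 13.4). That argues for adding it to an amendment made for other reasons. The clinical downside is that patients in the band stay on drug longer. The same edit can correct the baseline cross-reference for Part A, where the enrollment counts are in Inclusion Criterion #3 and #4 is history of response.
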